# **DOCUMENT HISTORY**

Document	Date of Issue	Approver(s)	Summary of Change
im027040- protamend05	22-Sep-2022	Head of Clinical Development Immunology and Fibrosis	
 
Updated BMS Japan address.
 
Added clarifying sentence in Section 5.1 and 7.3.1
 
Updated header and footnote c in Table 7.
 
Added clarifying text in Section 10.4.4.
 

im027040- admlet07	13-Jun-2022	Clinical Scientist Team Lead BMS Immunology & Fibrosis Clinical Development	• Incorporated into im027040-protamend05.
im027040- admlet06	02-May-2022	Clinical Scientist Team Lead BMS Immunology & Fibrosis Clinical Development	• Incorporated into im027040-protamend05.
im027040- admlet05	22-Feb-2022	Clinical Scientist Team Lead BMS Immunology & Fibrosis Clinical Development	• Incorporated into im027040-protamend05.
im027040- admlet04-cn- specific	22-Dec-2021	Medical Monitor	• Clarified 2 separate consistency errors in im027040-protamend01-cn (China-specific).
im027040- protamend04	21 Dec 2021	Head of Immunology & Fibrosis Clinical Development Bristol-Myers Squibb	
 
Revised the PET tracer substudy to allow incorporation of participants with PF-ILD
 
Clarified phrasing in inclusion and exclusion criteria
 
Added 2 secondary endpoints evaluating the effect of BMS-986278 treatment
 

im027040- protamend01-cn China-specific	01 Nov 2021	Head of Immunology & Fibrosis Clinical Development Bristol-Myers Squibb	
 
Removed biomarker assessments, Additional Research, and intensive PK substudy for all participants enrolled in mainland China.
 
Clarified objectives and endpoints for mainland China.
 

im027040- admlet03	13 Apr 2021	Clinical Trial Physician	• Incorporated into im027040-protamend04

Approved v 6.0 930149229 6.0

Protocol Amendment No.: 05 Date: 22-Sep-2022

Jaie. 22-Sep-2022

Document	Date of Issue	Approver(s)	Summary of Change
im027040- revprot03a-tw- specific	15 Mar 2021	Clinical Program Lead - Fibrosis	Removed eCOA measures from main study and optional treatment extension      Clarified language around dosing
			time and day collection prior to PK visits
im027040- admlet02	04 Mar 2021	Clinical Trial Physician	• Incorporated into im027040- protamend04
im027040- revprot03	14 Jan 2021	Clinical Program Lead - Fibrosis	Updated sections throughout protocol to allow participants with PF-ILD to remain on stable background therapies.
			Clarified restriction on concomitant use of anti-fibrotics during the main study.
			• Updated screening period from 28 to 42 days.
			Updated several inclusion and exclusion criteria.
			Added COVID-19-related risk assessment.
			Added language for collecting AEs and SAEs related to COVID-19.
			Added serum collections for possible assessments of SARS-CoV-2 serologic status and related exploratory objective and endpoint.
			Added clinical laboratory sampling on Day 1 of the OTE.
			Updated study treatment discontinuation criteria.
			Added requirement to record date and time of last study treatment administration prior to PK study visits.
			Modified language referring to number of participants enrolled per treatment arm in the PK substudy.
			Revised language throughout protocol to provide sites more flexibility regarding order and timing of study procedures.

Document	Date of Issue	Approver(s)	Summary of Change
			Clarified definitions for orthostatic hypotension and orthostatic tachycardia.
			• Clarified the Hepatitis B virus DNA serology testing.
			Added AE intensity definitions.
			• Updated definitions for Full Analysis Set and Safety populations.
			Clarified requirement for review of dosing diaries.
			Added section for OTE rationale.
			Revised language on nintedanib nonclinical toxicology.
			Updated contact information for Clinical Trial Physician/Medical Monitor.
			Added Clinical Scientist name and contact info to title page.
im027040- amend02-site- specific	22 Sep 2020	Study Director	• Incorporated into im027040-revprot03
im027040- admlet01	17 Sep 2020	Clinical Trial Physician	• Incorporated into im027040-revprot03
im027040- revprot02a-uk- specific	11 Sep 2020	Clinical Program Lead - Fibrosis	• Incorporated into im027040-revprot03
im027040-	25 Jun 2020		Changed Medical Monitor
revprot02		Clinical Program Lead - Fibrosis	Added an optional treatment extension for IPF and PF-ILD participants who complete the main study
			Extended intensive PK substudy participation to the PF-ILD cohort

Protocol Amendment No.: 05 Date: 22-Sep-2022

Approved v **6.0** 930149229 6.0

Document	Date of Issue	Approver(s)	Summary of Change
			and adjusted the number of participants to be included
			Clarified the posttreatment HRCT requirement for the main study
			• Added spirometry measurements to Week 20 in the main study
			• Removed the FEF25-75 test from spirometry parameters
			Added a sparse PK sample collection at the Week 4 visit in the main study
			Modified the secondary and exploratory endpoints
			Added a statistical analysis for the PF-ILD cohort once the cohort completes the main study
			• Incorporated changes requested by  Ethics  Committee:
			
 
Added "end of study" definition
 
Excluded participants with total bilirubin greater than 1.5 x ULN and specified the range permitted for those with Gilbert's syndrome
 

			
 
Excluded participants with history of allergy to BMS- 986278 or history of significant drug allergy
 

			
 
Clarified additional ECG         assessments to be performed as         clinically indicated
 

			
 
Added a caption title to create
 
Table 10
 

im027040- amend01-site- specific	12 Mar 2020	Clinical Development Team Lead - Fibrosis	Not applicable. PET-Tracer substudy will be conducted at selected US sites.
im027040- revprot01	24 Feb 2020	Clinical Development	Added Medical Monitor
revprotor		Therapeutic Area Head, Fibrosis Bristol-Myers Squibb	

Added eligibility check

Added pregnancy testing for women

		Diistor-iviyets squito	< 55 years of age
		Head of IMD Regulatory & Pharmaceutical Sciences	Removed Study     Acknowledgement/Disclosure page
		Bristol-Myers Squibb	Clarified drug dispensing frequency and treatment compliance check
			Clarified when vital signs and orthostatic BP and HR will be measured

Protocol Amendment No.: 05 Date: 22-Sep-2022

e: 22-Sep-2022

Document	Date of Issue	Approver(s)	Summary of Change
			Removed approximate blood volumes to be collected throughout the study
			Clarified when to withhold study treatment
			Clarified "progression" definition for PF-ILD inclusion criteria
			Lowered age limit for PF-ILD cohort
			Broadened language about excluding significant lung disease from both cohorts
			Permitted stable DMARD use for PF-ILD participants
			Added HBcAb and pregnancy test, and removed cannabinoids from Laboratory Assessments
Original Protocol	07 Jan 2020	Clinical Development Therapeutic Area Head, Fibrosis Bristol-Myers Squibb	Not applicable
		Head of IMD Regulatory & Pharmaceutical Sciences Bristol-Myers Squibb	

#### **OVERALL RATIONALE FOR PROTOCOL AMENDMENT 05**

The primary purpose of this protocol amendment is to implement the following changes:

- Add clarification that the optional treatment extension (OTE) for the IPF and PF-ILD cohorts will be unblinded after the respective database locks occur at the end of Week 26 of the main study for each cohort.
- Clarify that select efficacy (eg, FVC) and safety data from the OTE portion of the IPF cohort will also be reviewed by the sponsor at the time of the IPF cohort main study database lock.
- Implement protocol changes from administrative letters 5, 6, and 7.
- Edits made to ensure clarity and alignment between sections and with previous protocol versions.

All changes applied to the body were applied to the synopsis, as necessary, although not all synopsis changes are included in the table below.

Generally, only major additions and deletions are provided in this summary of changes, and all minor grammatical, formatting, rephrasing, stylistic changes, or clarifications, as well as reorganizational changes are not included.

SUMMARY OF KEY CHANGES OF PROTOCOL AMENDMENT 05		
Section Number & Title	Description of Change	Brief Rationale
Cover Page	Updated BMS Study Director as described in im027040-admlet07 and updated BMS Japan address	To update the Study Director following a change in personnel and to change BMS address in Japan
2 Schedule of Activities, Table 2	Updated footnote c as described in im027040-admlet06	To rectify an inconsistency in the previous protocol version
5.1 Overall Design	Added clarifying sentence	To clarify that the OTE phase for IPF and PF-ILD cohorts will be unblinded after database lock at Week 26

Protocol Amendment No.: 05

Section Number & Title	Description of Change	Brief Rationale
7.3.1 Maintaining the Blind	Added clarifying sentence	Add clarification that the optional treatment extension (OTE) components of the study for the IPF and PF-ILD cohorts will be unblinded after the respective database locks occur at the end of Week 26 of the main study for each cohort. As such, when the IPF OTE becomes unblinded upon DBL for the IPF main study, the PF-ILD cohort will remain blinded until database lock at Week 26 for PF-ILD main study.
9.5 Pharmacokinetics	Corrected inconsistency between the previous protocol version and the participant's document as described in im027040-admlet05	To clarify that participants in the main study should also record date and time of morning and evening doses on the day prior to Week 12 study visit in addition to those of Weeks 4 and 26
9.5.2 Intensive PK Substudy, Table 7	Updated header and footnote c	To rectify an inconsistency in the previous protocol version
10.4.4 Other Analyses	Added clarifying text	Add clarification that the optional treatment extension (OTE) components of the study for the IPF and PF-ILD cohorts will be unblinded after the respective database locks occur at the end of Week 26 of the main study for each cohort.
APPENDIX 8: Site-specific Protocol for Qualified PET-tracer Sites in US	Updated screening period	To change screening period of the PET-tracer substudy
Section 1.3, Table 1 Section 4.1, Figure 1		

Protocol Amendment No.: 05

#### 1 PROTOCOL SUMMARY

# 1.1 Synopsis

Protocol Title: A Multicenter, Randomized, Double-blind, Placebo-controlled, Phase 2 Study of the Efficacy and the Safety and Tolerability of BMS-986278 in Participants with Pulmonary Fibrosis

#### **Short Title:**

Phase 2 Study of the Efficacy and Safety of BMS-986278 in Pulmonary Fibrosis

#### **Study Phase:**

Phase 2

#### **Rationale:**

Idiopathic pulmonary fibrosis (IPF) is a chronic, progressive, and fatal lung disease that is characterized by worsening dyspnea, cough, and progressive loss of lung function due to scar formation in the lung. The diagnosis of IPF is based on integration of clinical, radiologic, and when available, pathologic data to exclude known causes of usual interstitial pneumonia (UIP) (eg connective tissue disease or environmental exposure). BMS-986278, a lysophosphatidic acid receptor 1 (LPA1) antagonist, is being developed for the treatment of patients with IPF. Lysophosphatidic acid (LPA) is a bioactive lysophospholipid that regulates numerous aspects of cellular function and has been recognized as a mediator of wound healing and tissue fibrosis. LPA signals through a family of G protein-coupled receptors designated LPA1-6. LPA1 antagonism inhibits the production of profibrotic matrix proteins, such as collagen.

Beyond IPF, some patients with other forms of chronic fibrotic interstitial lung disease (ILD) develop a progressive phenotype characterized by worsening respiratory symptoms, lung function, progressive fibrosis on imaging and early mortality. There is a high unmet need for effective and tolerable treatments for patients with non-IPF, fibrotic ILD that exhibit disease progression. Because of the clinical and pathophysiological similarities among these diseases, it has been suggested that such disorders have a common pathobiologic mechanism regardless of the cause – with resultant progressive lung fibrosis – and thus could have a response to similar treatment as IPF. Indeed, in the recently published INBUILD trial, patients with non-IPF, progressive fibrotic ILD (PF-ILD) with diverse etiologies were treated with nintedanib or placebo. Those treated with nintedanib had slower progression of lung fibrosis than those who received placebo, as demonstrated by a lower annual rate of decline in forced vital capacity (FVC) over the 52-week study period. The absolute treatment effects in the PF-ILD cohort were similar in magnitude to those observed in the pivotal INPULSIS trials that led to approval of nintedanib for treatment of IPF and based on data from the INBUILD trial, a number of health authorities have also approved nintedanib for patients with PF-ILD.

This study is the first evaluation of BMS-986278 in participants with pulmonary fibrosis. This study is designed to provide an initial evaluation of the efficacy of BMS-986278 in participants with IPF, further demonstrate the safety of BMS-986278, and provide information on

Protocol Amendment No.: 05

pharmacokinetics (PK) of BMS-986278 in participants with IPF. In addition, a secondary cohort consisting of PF-ILD participants will be enrolled, with the same schedule of activities and endpoints, in order to assess safety, tolerability, and efficacy of BMS-986278 in PF-ILD. The 2 cohorts (and subsets within the cohorts) will be analyzed separately.

## **Study Populations:**

Eligible participants will be males and females 40 years of age and older with a diagnosis of IPF (primary cohort) or males and females 21 years of age and older with a diagnosis of PF-ILD (secondary cohort). Females must not be of childbearing potential, defined as being postmenopausal or surgically sterilized.

The primary cohort includes participants with IPF. Background standard of care (SOC) with either pirfenidone or nintedanib therapy is allowed. Randomization will be stratified by country (non-Japan versus Japan), and by concomitant use of approved IPF therapy (pirfenidone versus nintedanib versus none).

A separate population of participants with PF-ILD, will be enrolled in a secondary cohort. Although there is no global standard of care (SOC) for PF-ILD, participants in the PF-ILD cohort will be allowed to remain on stable background therapies commonly used as part of their usual care, including nintedanib, pirfenidone, and/or select immunosuppressive medications. Randomization within the PF-ILD cohort will be stratified by UIP pattern of lung injury (present versus absent) and by category of background therapy (ILD-targeted immunosuppression [ie, azathioprine, mycophenolate mofetil, mycophenolic acid, and/or tacrolimus] alone versus antifibrotics [nintedanib, pirfenidone] with or without ILD-targeted immunosuppression versus no ILD-targeted immunosuppression or anti-fibrotics).

In order to augment knowledge about safety, tolerability, and efficacy of BMS-986278 in lung fibrosis patients, an optional treatment extension (OTE) will be offered to those participants that complete the 26-week main study.

## **Objectives and Endpoints:**

Objective	Endpoint(s)		
Primary			
To evaluate the rate of change in percent predicted forced vital capacity (ppFVC) from baseline to Week 26 in IPF participants randomized to receive BMS-986278 at 30 mg or 60 mg twice daily (BID) compared to those randomized to receive placebo.	Rate of change in ppFVC (%) from baseline to Week 26 in IPF participants		
Secondary			
To evaluate the safety and tolerability of  DNG 09(278 d. 1.26 d.	Adverse events (AEs)		
BMS-986278 through 26 weeks of treatment by comparing results observed in participants with	• Serious AEs (SAEs)		
IPF and PF-ILD randomized to receive BMS-986278 at 30 mg or 60 mg BID with those	AEs leading to early discontinuation of study treatment		
	Treatment-emergent deaths		

Protocol Amendment No.: 05

Objective	Endpoint(s)

 
who receive placebo. The IPF and PF-ILD cohorts will be analyzed separately.
 
To evaluate the rate of change in ppFVC from baseline to Week 26 in PF-ILD participants randomized to receive BMS-986278 at 30 mg or 60 mg twice daily (BID) compared to those
 
	
 
Clinical laboratory findings
 
Electrocardiograms (ECGs)
 
Vital signs
 
Physical exam findings
 
Rate of change in ppFVC (%) from baseline to Week 26 in PF-ILD participants
 

randomized to receive placebo.  To evaluate the effect of treatment with BMS-986278 on clinical assessments of lung fibrosis in IPF and PF-ILD participants randomized to receive BMS-986278 at 30 mg or 60 mg BID compared with participants randomized to receive placebo through Week 26. The IPF and PF-ILD cohorts will be analyzed separately.	
 
Proportion of participants with ≥ 10% absolute decline in ppFVC (%) at Weeks 4, 8, 12, 16, 20, and 26
 
Proportion of participants with > 0% change in ppFVC at Weeks 4, 8, 12, 16, 20, and 26
 
Time to first acute exacerbation
 
Time to first ≥ 10% absolute decline in ppFVC (%)
 
Absolute change in FVC (mL) from baseline to Week 26
 
Absolute change in single-breath diffusing capacity of carbon monoxide (DLCO SB) (mL/min/mmHg) (corrected for hemoglobin) from baseline to Week 26
 
Absolute change in percent predicted single-breath diffusing capacity of carbon monoxide (DLCO SB) (mL/min/mmHg) (corrected for hemoglobin) from baseline to Week 26
 
Absolute change in percent predicted single-breath diffusing capacity of carbon monoxide (ppDLCO SB) (%) (corrected for hemoglobin) from baseline to Week 26
 
Change in walking endurance/distance from baseline at Week 26 as measured using the 6-minute walk test (6MWT)
 
Proportion of participants with acute exacerbations of lung fibrosis defined as an acute, clinically significant, respiratory deterioration characterized by evidence of new widespread alveolar abnormality, as follows:
 
1. Acute worsening or development of dyspnea (< 1 month duration)
 
2. Imaging with new bilateral ground-glass opacity and/or consolidation superimposed on a background pattern of lung fibrosis
 
3. Respiratory deterioration not fully explained by cardiac failure or fluid overload
 

To characterize the pharmacokinetics (PK) of BMS-986278 in IPF participants.	Cmax, Tmax, and AUC(0-8) on Day 1 and Week 4 and Ctrough on Week 4 and Week 12 of intensive PK substudy

Protocol Amendment No.: 05

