#### **Overall Design:**

This is a Phase 2 randomized, double-blind, placebo-controlled clinical study investigating the efficacy and the safety and tolerability of BMS-986278 in participants with pulmonary fibrosis. In the primary cohort, a total of approximately 240 participants with IPF will be randomized to receive 30 mg or 60 mg BMS-986278 twice daily (BID) or placebo BID at a ratio of 1:1:1 for 26 weeks in the main study. Stable SOC background therapy for IPF with either nintedanib or pirfenidone will be allowed.

In the secondary cohort, a population of participants with PF-ILD, will be randomized and analyzed separately from the IPF cohort. In the PF-ILD cohort, a total of approximately 120 participants with PF-ILD will be randomized to receive 30 mg or 60 mg BMS-986278 BID or placebo BID at a ratio of 1:1:1 for 26 weeks. Participants with PF-ILD will be allowed to remain on stable background therapies commonly used as part of their usual care, including nintedanib, pirfenidone, and/or select immunosuppressive medications.

IPF and PF-ILD participants receiving 30 mg or 60 mg (or placebo) BMS-986278 BID in the main study who meet low blood pressure (BP) criteria may be dose reduced to 10 mg BMS-986278 BID (or placebo for 10 mg BID) (refer to Section 5.1.2.1).

A study schematic is provided in Section 2, and in Figure 1 for the IPF cohort and Figure 2 for the PF-ILD cohort. Following a screening period of up to 42 days, eligible participants with IPF or PF-ILD will be randomized to receive 1 of 2 dose levels of BMS-986278 (30 mg or 60 mg BID) or placebo for 26 weeks. In the IPF cohort, randomization will be stratified by country (non-Japan versus Japan) and according to concomitant use of approved IPF therapy (pirfenidone versus nintedanib versus none). In the PF-ILD cohort, randomization will be stratified by UIP lung injury pattern (present versus absent) and by category of background therapy (ILD-targeted immunosuppression [ie, azathioprine, mycophenolate mofetil, mycophenolic acid, and/or tacrolimus] alone versus anti-fibrotics [nintedanib, pirfenidone] with or without ILD-targeted immunosuppression versus no ILD-targeted immunosuppression or anti-fibrotics).

All participants randomized in the main study will undergo safety, functional, quality-of-life, laboratory, PK, and biomarker assessments according to the Schedule of Activities (Table 1).

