	Screening			Day 8	Day 29	Day 57	Day 85	Day 113	Day 141	Day 183	treatment follow-up c (28 ± 7 days after Week 26)	
	(Day -42 to Day -1)	Day 1	Day 2 b	Week 1 (± 3 days)	Week 4 (± 3 days)	Week 8 (± 5 days)	Week 12 (± 5 days)	Week 16 (± 5 days)	Week 20 (± 5 days)	Week 26 (+ 5 days)		Notes
Blood samples for biomarkers						See	notes.					See Section 9.6 and Table 9 for further details.
Efficacy-related	l Assessment	ts										
HRCT	X									X		Screening HRCT must be read by central reader before randomization. See Section 9.1.3 and Section 6.4.1 for further details.
Spirometry e	X	X			X	X	X	X	X	X		See Section 9.1.1 for further details.
DLCO SB	X	X					X			X		See Section 9.1.2 for further details.
Clinical Outcom	ne Assessme	nts (C	COAs	)	•							
L-PF		X					X			X		IC '11 COA 1 111
SGRQ		X					X			X		If possible, eCOAs should be administered using the electronic
UCSD SOBQ		X					X			X		device prior to other study related procedures (except for the Day 1
Cough VAS		X					X			X		visit where COAs should be
PGI-S		X					X			X		administered after vital signs and ECG).
PGI-C							X			X		1200).
6MWT		X					X			X		If possible, to be administered after eCOAs.  Separate instructions on the 6MWT will be provided.  See Section 9.1.4.6 for further details.

Protocol Amendment No.: 05

Table 1: Schedule of Activities for Study IM027040 (Main Study)

					Treat	ment (Da	y 1 to W	eek 26 ) a			Post-	
	Screening			Day 8	Day 29	Day 57	Day 85	Day 113	Day 141	Day 183	treatment	
	(Day -42 to Day -1)	Day 1	Day 2 b	Week 1 (± 3 days)	Week 4 (± 3 days)	Week 8 (± 5 days)	Week 12 (± 5 days)	Week 16 (± 5 days)	Week 20 (± 5 days)	Week 26 (+ 5 days)	follow-up c (28 ± 7 days after Week 26)	Notes
O2 Titration Test	X											An oxygen titration test is required for all participants at screening.
Study Treatmer	nt/Concomit	ant N	1edic a	ation								

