#### 9 STUDY ASSESSMENTS AND PROCEDURES

Study procedures and timing are summarized in the Schedule of Activities in Table 1 for the main study and in Table 2 for the OTE.

Every effort must be made to ensure that the same evaluator(s) completes the assessment for each participant. If the evaluator(s) is unable to complete the evaluation, then a qualified individual with overlapping experience may perform the assessment. It is preferable that assessments be performed at approximately the same time of day throughout the duration of the study. Day 1 (Randomization) assessments must be performed per protocol (SOC assessments may not be used for baseline). Procedures not specified in the protocol that are part of standard care may be performed if they do not interfere with study procedures; any data arising from such procedures are not to be reported in the eCRF.

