### Timing of Spirometry:

The spirometry test is to be performed prior to the morning dose, preferably at approximately the same time  $(\pm 1 \text{ h})$  at every visit in which spirometry is performed. The spirometry test is permitted to be completed up to 3 days prior to the scheduled study visit.

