## 10.4.1.2 Secondary Efficacy Endpoints

All secondary analyses will be based on the FAS population. As appropriate, continuous secondary endpoints will be analyzed using mixed model repeated measures (MMRM) with a random effect for participant and fixed effects for treatment, visit, treatment-by-visit interaction, and baseline stratification factors. The baseline value of the endpoint being tested will be added into the model as a covariate. In addition, as appropriate analysis of covariance models will be used to analyze continuous secondary endpoints with treatment and factors used for randomization as fixed effects. The baseline value will be added into the model as a covariate.

Cochran-Mantel-Haenszel tests will be used to compare dichotomous endpoints between either BMS-986278 dose group vs placebo.

The Kaplan-Meier product limit method will be used to estimate the survival curves for time-to-event endpoints. Treatment comparisons between each BMS-986278 dose group and placebo will be performed using the log-rank test stratified by baseline stratification factors.

The PF-ILD cohort will be analyzed separately from the primary study cohort of IPF. The PF-ILD statistical analysis methods will be similar to IPF cohort. The details will be described in the SAP.

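### Spirometry and DLCO SB are taken at both screening and Day 1, but the secondary models name one baseline value; adding the screening value as a second covariate would buy some precision at little cost.

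*Combined protocol and SAP*

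**What the plan says.** The secondary endpoints listed in the synopsis (Section 1.1) include "Absolute change in FVC (mL) from baseline to Week 26".

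In Table 1 (Section 2) the spirometry row is marked at screening and on Day 1 ("Spirometry e X X") and then at Weeks 4, 8, 12, 16, 20 and 26. The DLCO SB row, with the note "See Section 9.1.2 for further details", is marked at screening, Day 1, Week 12 and Week 26. The gap between the two early measurements can be long: "Following a screening period of up to 42 days". On Day 1, as at other visits, "The spirometry test is to be performed prior to the morning dose".

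Section 6.1 makes ppFVC and ppDLCO SB entry criteria, so essentially every randomised participant should have a screening value of each.

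For the MMRM, Section 10.4.1.2 states: "The baseline value of the endpoint being tested will be added into the model as a covariate". For the ANCOVA it states: "The baseline value will be added into the model as a covariate". Neither sentence says how baseline is derived. The nearest guidance is in Section 9: "Day 1 (Randomization) assessments must be performed per protocol (SOC assessments may not be used for baseline". That points to Day 1 but is not a derivation rule. Section 10.4 describes itself as a summary and leaves detailed specifications to the SAP. Nothing in the protocol puts the screening value into an efficacy model.

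**The concern.** A single spirometry or DLCO reading contains measurement error. When change is measured from one Day 1 reading, the error in that reading enters every change, and adjusting for the same reading takes out only part of it. The screening value comes before any treatment and carries further information on where the participant started. As a prespecified covariate it cannot bias a randomised comparison, and it narrows the interval whenever it predicts Week 26 beyond what Day 1 already predicts.

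At stake is the width of the confidence intervals for four secondary change-from-baseline endpoints: ppFVC, FVC (mL), DLCO SB and ppDLCO SB. The data will be collected anyway.

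**Working it through.** **Inputs from Section 10.1.** SD of ppFVC change 6.5; difference 2.5; 80 per arm; two-sided 95% intervals; 80% completion.

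**Assumed, not in the documents.** Per-visit test-retest SD *s* of 2, 3 or 4 points; between-participant SD 15; gap from screening to Day 1 of 7, 21 or 42 days; pre-treatment slope either unrelated to the on-study slope or equal to it.

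**1. The plan's own figure.** Half-width = 1.96 × 6.5 × √(2/n).
- n = 60: 2.33, giving 0.17 to 4.83
- n = 80: 2.01, giving 0.49 to 4.51
- n = 100: 1.80, giving 0.70 to 4.30

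All three rows of Table 10 reproduce, so 6.5 acts as the per-participant SD of change.

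**2. Model.** Time is in units of 26 weeks (182 days) and g = gap/182.
- Day 1: X1 = a + e1
- Screening: X0 = a − g·b0 + e0
- Week 26: Y = a + b + e2

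Var(a) = 15² = 225 and each error has variance s². The SD of change is held at 6.5, so Var(b) = Var(b0) = 42.25 − 2s².

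**3. Residual variance with Day 1 alone.** V1 = 225 + Var(b) + s² − 225²/(225 + s²).
- s = 2: 263.25 − 221.07 = 42.18
- s = 3: 258.25 − 216.35 = 41.90
- s = 4: 251.25 − 210.06 = 41.19

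**4. Residual variance with Day 1 and screening.** V2 = 225 + Var(b) + s² − c′S⁻¹c. S has diagonal 225 + s² and 225 + s² + g²Var(b), and off-diagonal 225. c = (225, 225 − k·g·Var(b)), with k = 0 for unrelated slopes and k = 1 for equal slopes.

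Example, s = 4, gap 42 days, k = 0: the diagonal of S is 241 and 241.55, and its determinant is about 7,588. Then c′S⁻¹c = 50,625 × 32.55/7,588 ≈ 217.15, so V2 = 251.25 − 217.15 = 34.10. The reduction is 1 − 34.10/41.19 = 17.2%.

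**5. Fall in residual variance (gap 7 / 21 / 42 days).**

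| s | Unrelated slopes | Equal slopes |
|---|---|---|
| 2 | 4.6 / 4.4 / 3.8% | 2.0 / 0.0 / 3.8% |
| 3 | 10.1 / 9.9 / 9.4% | 8.0 / 4.6 / 1.2% |
| 4 | 17.5 / 17.4 / 17.2% | 16.6 / 14.8 / 12.2% |

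With equal slopes the screening value informs both the starting level and the slope, and these pull its coefficient in opposite directions. At s = 2 and 21 days they cancel.

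For s = 4, a between-participant SD of 10 gives about 10.8–15.9%, and 20 gives about 12.8–18.1%.

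**6. In trial terms.** At s = 4 and 80 per arm the half-width goes from 1.96√(2 × 41.19/80) = 1.99 to between 1.81 and 1.86. Equivalent sample size is 80/(1 − reduction): 80 to 84 at s = 2, 81 to 89 at s = 3, 91 to 97 at s = 4. With 64 completers (80% of 80), the best case at s = 2 is 64/(1 − 0.046) ≈ 67.

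**7. Ceiling.** If the two early readings and the Week 26 reading were equally correlated (ρ), V2/V1 = (1 + 2ρ)/(1 + ρ)². This never falls below 3/4, so the reduction cannot exceed 25%.

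**The case against.** The strongest reply is that nothing here is an error. One baseline covariate is a conventional and valid model, and the gain is confined to secondary endpoints. That stands, and the point is offered only as an improvement.

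The size rests on a test-retest SD that the documents do not give. With the SD of change at 6.5, the share of its variance due to measurement noise is 2s²/42.25: 19% at s = 2, 43% at s = 3, 76% at s = 4. The last leaves a true-change SD of only √10.25 = 3.2, and nothing in the documents supports it. Section 10.3.1 assumes linear decline within each participant on study; carried back to screening, that favours the equal-slopes column. Both points stand as limits on the size.

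The screening value may also be an imperfect replicate. Section 5.1.1 lets some routine-care procedures serve for screening, and Section 6.4.1 allows repeats. This does not bias the comparison, but it may shrink the gain, and the fix needs a rule for such values.

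Four stronger readings are tempting, and the documents do not support them.
- A reader might infer that the screening data could remove the measurement error. They remove part of the baseline component only; Week 26 error and true variation in decline remain.
- A reader might infer a biased treatment effect. Error in a baseline covariate does not bias a randomised contrast.
- A reader might infer that the plan settles on Day 1 and rules out screening. Baseline is never formally defined, and detail is left to the SAP.
- A reader might extend the point to the primary analysis or to every continuous endpoint. The primary slope model in Section 10.4.1.1 lists no baseline ppFVC covariate, and the 6MWT is not performed at screening.

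**Conclusion.** The point holds as a cheap gain in precision, not as a fault in validity. For ppFVC in the IPF cohort, residual variance in the Week 26 contrast would fall by roughly 0–5%, 1–10% or 12–17.5% for a test-retest SD of 2, 3 or 4. This assumes a change SD of 6.5, a between-participant SD of 15, and screening 7 to 42 days before Day 1. At the low end the gain is negligible.

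No figure can be given for FVC (mL), DLCO SB or ppDLCO SB, because the documents state no SD for them. The gain would be larger for DLCO if its test-retest error is large relative to true 26-week change, but that is conjecture. The documents also give no SD for the PF-ILD cohort (40 per arm), so the ppFVC percentages carry over only if its variances are similar.

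**What to change.** In Section 10.4.1.2, and in the SAP before first unblinding:
- State that Day 1 is the baseline for defining change in ppFVC, FVC (mL), DLCO SB and ppDLCO SB.
- Add the last screening value of the same measure as a second prespecified continuous covariate in both the MMRM and the ANCOVA. Entering both values, rather than their mean, lets the data set the weights when the gap is long.
- Where a screening value is missing or was not obtained under the protocol, impute it without regard to treatment arm, for example from the Day 1 value, so that no participant drops out of the model.

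The cost is one degree of freedom, one line in each model statement and a simple imputation rule. No visit or test is added. The gain for ppFVC may be close to nil if test-retest error is small.
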